- THS 2.2 Arm: 80 subjects, *ad libitum* use of the product.
- CC Arm: 40 subjects, *ad libitum* use of their preferred CC brand.
- SA Arm: 40 subjects who will abstain from smoking.
Subjects will be informed of their randomized study arm by the study site collaborator on Day 1 prior to 06:30 AM.

- Exposure period (from Day 1, 06:30 AM until Day 5, 11:00 PM):
The exposure period will consist of 5 days of *ad libitum* use of the assigned product between 06:30 AM and 11:00 PM in THS 2.2 and CC arms. Use of any tobacco/nicotine containing product other than the assigned product will not be allowed and may, at the discretion of the Investigator, result in the subject withdrawal from the study.

Subjects in the SA arm will be asked to abstain from smoking any nicotine/tobacco containing product and will not be provided with medication to support SA. Subjects will be provided with psychological support during the period of smoking abstinence.

The end of the 24-h urine collection period for Day 5 will end in the morning on Day 6 prior to Discharge.

- Day of Discharge (Day 6) (from Day 5, 11:01 PM to time of Discharge):
Procedures of Discharge, including but not limited to laboratory parameters, will be conducted to discharge the subject from the clinic after 9 days in a confined setting. Use of CC will be allowed on Day 6, but only after spirometry has been performed.
- Safety follow-up period (from the time of Discharge on Day 6 to Day 13):
After time of Discharge, subject will enter a 7-day safety follow-up during which there will be recording of spontaneously reported new AEs/SAEs and the active follow-up of ongoing AEs/SAEs by the study site. In general, all AEs will be followed until resolved, stabilized (i.e., no worsening of the event), or a plausible explanation for the event has been found. The end of the study is defined as the time of Discharge on Day 6 plus 7-day follow-up period.

During the study, any subjects who want to quit smoking will be encouraged to do so, and will be referred to medical services and will be withdrawn from the study. This is applicable for all subjects during screening to the baseline period and for subjects allocated to THS 2.2 or CC arms during the exposure period.

Study Population and Main Criteria for Inclusion and Exclusion:

160 female or male smoking, healthy Japanese adult subjects meeting the following main inclusion criteria:

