7.8.3.2 Assessment of Cough

Subjects will be asked to assess the respiratory symptom ‘cough’ on a VAS, on 3 Likert scales, and with an open question on a daily basis during the confinement period from Day 0 to Day 6. On each day, cough assessment has to be done prior to product use but no later than 10:00 AM.

Subjects will be asked if they have experienced a regular need to cough, (e.g., whether they have coughed several times in the previous 24-hours prior to assessment). If the answer is ‘yes’, subjects will be asked to complete a VAS, 3 Likert scales, and to answer the open question.

On the VAS, subjects will assess how bothersome their cough was during the previous 24-hours. The VAS ranges from ‘not bothering me at all’ to ‘extremely bothersome’.

Furthermore, subjects will assess the intensity and frequency of cough and the amount of sputum production during the previous 24-hours on Likert scales.

The intensity of cough will be assessed on a 5-point Likert scale ranging from 1 to 5, with 1 = very mild - 2 = mild - 3 = moderate - 4 = severe - 5 = very severe.

Confidentiality statement: Data and information contained in this document are considered to constitute trade secrets and confidential commercial information, and the legal protections provided to such trade secrets and confidential information are hereby claimed under the provisions of applicable law. No part of this document may be publicly disclosed without the written consent of Philip Morris Products S.A.

The frequency of cough will be assessed on a 5-point Likert scale ranging from 1 to 5, with 1 = rarely - 2 = sometimes - 3 = fairly often - 4 = often - 5 = almost always.

The amount of sputum production will be assessed on a 4-point Likert scale ranging from 0 to 3, with 0 = no sputum - 1 = a moderate amount of sputum - 2 = a larger amount of sputum - 3 = a very large amount of sputum.

Finally, subjects will be asked with an open question if they want to share any other important observations with the study collaborator about their coughing.

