7.8.3.5 Minnesota Nicotine Withdrawal Scale (revised version)

The MNWS is a valid and reliable scale that has been used previously to examine signs and symptoms of withdrawal from cigarette smoking (Hughes and Hatsukami, 1986; Hughes and Hatsukami, 2008). It consists of two scales: a 'self-report scale' and an 'observer scale'.

For the purpose of this study, only the self-reporting scale will be used and filled-in by the subject. Furthermore, the subject's weight will not be recorded for the purpose of the MNWS. At the end of the assessment of the questionnaire, the subject's pulse rate will be recorded.

Subjects will be asked to rate the items for the previous 24-hours on a scale ranging from 0 to 4 (where 0 = none, 1 = slight, 2 = mild, 3 = moderate, 4 = severe).

The MNWS (revised version) will be completed on a daily basis from Day 0 to Day 6. On each day, MNWS has to be asked prior to product use but no later than 10:00 AM.

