9.2.3 Exposure Period (Days 1 to 5)

The tables in this Section show the assessments that will be performed during the confinement period (Day 1 to Day 5). Table 10 shows the assessments that will be performed on Day 1:

Table 10. Time Schedule – Day 1

Time	Blood sample	Procedures	Additional information
Start of procedure		Day 1	
		AE/SAE recording; concomitant medication	All day
		Support during smoking abstinence (SA arm only) if needed	All day
Before 06:30 AM		Subjects are informed of their assigned study arm.	
6:29 AM+/-20min		Analysis sample to be taken after final portion of urine has been added to Day 0 sampling bottle. Must be prior to first product use of Day 1	BoExp, creatinine, and Ames mutagenicity in 24-hour urine Risk markers: 8-epi-PGF2 α and 11- DTX-B2 Bio-banking for BoExp/ risk markers in 24-hour urine (if additional consent is obtained)

Confidentiality statement: Data and information contained in this document are considered to constitute trade secrets and confidential commercial information, and the legal protections provided to such trade secrets and confidential information are hereby claimed under the provisions of applicable law. No part of this document may be publicly disclosed without the written consent of Philip Morris Products S.A.

Time	Blood sample	Procedures	Additional information
Start of procedure		Day 1	
6:30 AM+/-20min		Start collection to Day 1 sampling bottle	
		Assessment of cough (VAS)	To be done prior to product use but not later than 10:00 AM
		MNWS questionnaire	To be done prior to product use but not later than 10:00 AM
		CO breath test	Within 15 minutes before first product use (for THS 2.2 and CC arms) or between 08:00 AM-09:30 AM (SA arm)
06:30 AM-11:00 PM		HST	In THS 2.2 and CC arms, HST SODIM [®] device has to be used for all product uses if compatible CCs are smoked
6:30 AM		Beginning of product use	
Before 10:00 AM		Breakfast	
10:00 AM-11:30 AM		Vital signs (blood pressure, pulse rate, respiratory rate)	At least 5 minutes in supine position prior to measurement
12:00 PM-01:30 PM		CO breath test	
Before 02:30 PM		Lunch	
04:00 PM-05:30 PM		CO breath test	
Afternoon		Snacks	
In the evening until 09:00 PM		Dinner	
08:00 PM-09:30 PM		CO breath test	
08:00 PM-09:30 PM	√	COHb in blood	
08:00 PM-09:30 PM	√	Nicotine, cotinine in plasma	
08:00 PM - 11:00 PM		MCEQ questionnaire (THS 2.2 and CC arms only), QSU-brief questionnaire	

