7.3.4 Minnesota Nicotine Withdrawal Scale (revised edition) Questionnaire

The MNWS (Hughes and Hatsukami 2008) is a 24 hour recall that will be completed by the subject him/herself daily on Day 0 to Day 6 prior to product use to reflect the previous days experience. Therefore although it is collected on Days 0 to 6 it will be reported as Days -1 to 5. Only the self-reported part of the MNWS will be used.

The self-reported part of the MNWS consists of the following 15 items which are rated over the last 24 hours on a scale of 0 to 4 (see Table 6). Higher scores indicate greater intensity on that scale.

The total scores will be derived by summing the individual item scores if all items are non-missing, otherwise the total score will be set to missing. The first total score calculated by summing the first 9 items is based on validated items, the second score is based on 6 extra items which are thought to have an impact on withdrawal but have not been validated.

**Table 6: Minnesota Nicotine Withdrawal Scale (Revised Edition)
Questionnaire Scores**

	Question	Total Score
1	Angry, irritable, frustrated.	1 and 2
2	Anxious, nervous.	1 and 2
3	Depressed mood, sad.	1 and 2
4	Desire or craving to smoke.	1 and 2
5	Difficulty concentrating.	1 and 2
6	Increased appetite, hungry, weight gain.	1 and 2
7	Insomnia, sleep problems, awakening at night.	1 and 2
8	Restless.	1 and 2
9	Impatient.	1 and 2
10	Constipation	2
11	Dizziness	2
12	Coughing	2
13	Dreaming or nightmares	2
14	Nausea	2
15	Sore throat	2

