12.6.3.1.3 Minnesota Nicotine Withdrawal Questionnaire

The MNWS will be administered daily from Days 0 to 6 for the assessment of Day-1 to Day 5 as it is a 24-hour recall questionnaire. The baseline will be the last assessment prior to 06:29 AM on Day 1.

All summaries, profiles and analysis will be presented for the THS 2.2, CC and SA arms.

The change from baseline will be calculated for both scores. The two scores, along with the change from baseline will be summarized. The answers to the individual questions, along with the two scores and changes from baseline will be listed.

The profiles of the raw means from baseline to Day 5 for the total scores will be produced.

The analysis will compare each post baseline timepoint for the two scores. A repeated measures ANCOVA model will be used with terms for baseline score, sex, average daily CC consumption over the last 4 weeks as reported during screening, product, time-point, and the interaction between product and time-point. No adjustment will be made for multiple comparisons.

The SAS code will be the same as described in Section 12.6.3.1.1 “Urge-to-Smoke Questionnaire of Smoking Urges Brief”.

LS means for each product along with the difference (THS 2.2 - CC) and (THS 2.2 – SA) with 95% CI will be presented in the tables. The SAS code above will also be amended appropriately to obtain the right comparisons.

All figures, summaries and analyses will be performed on the FAS.

The data will be presented in the below outputs, the TFL number refers to the TFL number in the accompanying TFL shell document:

TFL number	Title
FIGURES	
15.1.2.35	MNWS Total Scores Arithmetic Mean and 95% CI– FAS
15.1.2.36	MNWS Total Scores Arithmetic Least Squares Means and 95% CI– FAS
TABLES	
15.2.4.50	Descriptive Statistics of MNWS Total Scores – FAS
15.2.4.51	Analysis of MNWS Total Scores – FAS
LISTINGS	
15.3.6.12	Listing of MNWS Questionnaire Results and Changes from Baseline

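### The Day 1 withdrawal and cough forms, reported as Day 0, may be completed after the arm is disclosed, and the MNWS baseline form can differ between subjects

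*Protocol*

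**What the plan says.** **Disclosure.** The protocol synopsis and section 4.1 state: "Subjects will be informed of their randomized study arm by the study site collaborator on Day 1 prior to 06:30 AM". Section 6.3 says the same. Table 10 (section 9.2.3) puts the step first on Day 1, timed before 06:30 AM: "Subjects are informed of their assigned study arm". Table 9 tells the site to withhold the arm throughout Day 0.

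**Forms.** For the MNWS, protocol 7.8.3.5 says: "Subjects will be asked to rate the items for the previous 24-hours on a scale ranging from 0 to 4". On timing it adds: "On each day, MNWS has to be asked prior to product use but no later than 10:00 AM". For cough, 7.8.3.2 says: "On each day, cough assessment has to be done prior to product use but no later than 10:00 AM". In Table 10 both forms appear below the disclosure row, without a start time and with the note "To be done prior to product use but not later than 10:00 AM".

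**Day labels.** SAP 7.3.4 says of the MNWS: "Therefore although it is collected on Days 0 to 6 it will be reported as Days -1 to 5". SAP 7.3.6 relabels cough in the same way. The form completed on the morning of Day 1 is therefore the Day 0 score.

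**Baseline and its use.** SAP 12.1.4 and 12.6.3.1.3 define the MNWS baseline by the clock, as the latest assessment made before 06:29 AM on Day 1. For the analysis, 12.6.3.1.3 says: "A repeated measures ANCOVA model will be used with terms for baseline score, sex". It also plans change from baseline and a profile of raw means from baseline to Day 5.

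**The concern.** The protocol takes care to keep subjects unaware of their arm while baseline is recorded. For these two self-reports the protection can lapse: the form describing the last all-smoking day may be answered by someone who has just learned whether they must abstain. MNWS items include anxiety, irritability and craving, which that news could plausibly change.

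The arms also differ in what forces early completion. THS 2.2 and CC subjects must finish before first product use, which may be at 06:30 AM. SA subjects have no first use, so 10:00 AM is their only limit.

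At stake is the comparison of withdrawal symptoms between THS 2.2 and abstinence, a stated exploratory objective. It needs a baseline that comes from the same form for everyone and precedes knowledge of the arm.

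**Working it through.** The plan gives no figure to reproduce. The check sets the clock times against the SAP rules.

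**Inputs.** Disclosure on Day 1 before 06:30 AM (protocol 4.1, Table 10). Forms open until 10:00 AM (7.8.3.2, 7.8.3.5, SAP Table 16), with no earliest time. SA abstinence from 06:30 AM (6.2.3.3). Smoking hours 06:30 AM to 11:00 PM (4.1). MNWS baseline cut-off 06:29 AM (SAP 12.6.3.1.3).

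**Role of the Day 1 MNWS form, by completion time**

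| Form completed | Arm known? | MNWS baseline under the clock rule | Form reported as |
|---|---|---|---|
| Before disclosure and before 06:29 AM | No | This form | Day 0 |
| After disclosure, before 06:29 AM | Yes | This form | Day 0 |
| 06:29 AM or later, up to 10:00 AM | Yes, from 06:30 AM at the latest | Day 0 morning form, reported as Day -1 | Day 0 |

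All three rows comply with the protocol. In the second, the covariate is given with the arm known. In the third, the covariate comes from a form completed a day sooner, while the Day 1 form still supplies the reported Day 0 value. The SAP does not reconcile the clock rule with the day label.

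**Longest abstinence inside the Day 0 recall (SA arm)**

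- 06:30 to 10:00 AM = 3.5 h.
- Share of recall: 3.5 / 24 = 14.6%.
- Time since the last permitted cigarette: 11:00 PM to 10:00 AM = 11 h. Of this, 11:00 PM to 06:30 AM = 7.5 h is the night pause common to all arms, leaving 11 - 7.5 = 3.5 h.

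**Effect on the model.** Let *p* be the fraction of SA subjects in the second row, *d* the shift in their rating caused by knowing the arm, and *b* the baseline slope. The SA baseline mean moves by *p* × *d*, and the adjusted THS 2.2 - SA difference by about *b* × *p* × *d*. The documents give none of the three.

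**Contrast.** QSU-brief and MCEQ for Day 0 are completed between 08:00 and 11:00 PM on Day 0 (SAP 7.3.2, 7.3.3), before disclosure can occur. They do not share the problem.

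**The case against.** The strongest reply is that the clock rule already protects the baseline. Any form completed at or after 06:29 AM on Day 1 is excluded, so none of the 06:30 to 10:00 AM abstinence can enter the covariate or the change from baseline. This stands. Only a form completed between disclosure and 06:29 AM can carry knowledge of the arm into the model, and it contains no abstinence beyond the ordinary night.

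Three further points also stand. First, completing the forms before disclosure is permitted: protocol section 9 lets a procedure without a start time be done at any time, so 10:00 AM is an outer limit and the order of rows in Table 10 is not a rule. Second, use is ad libitum, so THS 2.2 and CC subjects may also delay first use and complete the forms late; what the SA arm lacks is anything that compels early completion. Third, SAP 12.6.4.5.6 plans only summaries and listings for cough, with no baseline covariate, so the covariate problem concerns the MNWS alone.

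A reader might infer that early abstinence biases the adjusted THS 2.2 - SA difference by slope times shift. With an assumed SA shift of 1 to 3 points and an assumed slope of 0.4 to 0.8, that gives 0.4 × 1 = 0.4 to 0.8 × 3 = 2.4 points on a 0 to 36 scale (9 items × 4). The documents do not support this. It treats the Day 1 form as baseline by its study-day label, whereas the SAP defines baseline by the clock, and neither the shift nor the slope is given anywhere.

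The clock rule does not fix everything. It leaves the second row of the table open, lets the baseline form vary between subjects, and does not stop a late form from being reported as Day 0.

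**Conclusion.** The gap is real but limited, and closing it is a cheap improvement. Some MNWS baselines may be given with the arm known, and others will come from the previous morning's form. The reported Day 0 MNWS and cough scores may reflect knowledge of the arm and, in the SA arm, at most 3.5 h of abstinence. How many subjects this affects depends on when sites actually administer the forms, which the documents leave open. The direction and size of any effect on the MNWS comparisons cannot be derived.

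The MNWS is exploratory, cough is descriptive, and neither enters the study's success criterion. The documents do not support saying that the Day 1 forms are always completed after disclosure, or that the adjusted arm differences are shown to be biased.

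**What to change.** - **Protocol 4.1, 6.3 and Table 10 (with the matching synopsis text):** on Day 1, subjects in all three arms complete the MNWS and cough forms on rising, before 06:29 AM and before being told their arm. Disclosure follows, still before 06:30 AM.
- **SAP 12.6.3.1.3:** name this form, reported as Day 0, as the MNWS baseline, so that the clock rule and the day label point to the same form.
- **SAP Table 16:** treat a Day 1 form completed after disclosure as a time deviation.

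No assessment is added, and subjects already rise for the void due at 06:29 AM (±20 minutes). The cost is a tighter early-morning sequence on Day 1.

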BoExp to nicotine	nicotine equivalents (NEQ) free nicotine, nicotine-glucuronide, free cotinine, cotinine-glucuronide, free trans-3'-hydroxycotinine, trans -3'-hydroxycotinine-glucuronide	nicotine	Urine
	nicotine	nicotine	Plasma
	cotinine	nicotine	Plasma

Primary Endpoints:

- To demonstrate the reduction of primary BoExp in smokers switching from CC to THS 2.2 as compared to those continuing to smoke CC.
- MHBMA, 3-HPMA, S-PMA (concentration adjusted to creatinine) in 24-hour urine, and COHb in blood (expressed as % saturation of hemoglobin) as measured on Day 5.

Confidentiality statement: Data and information contained in this document are considered to constitute trade secrets and confidential commercial information, and the legal protections provided to such trade secrets and confidential information are hereby claimed under the provisions of applicable law. No part of this document may be publicly disclosed without the written consent of Philip Morris Products S.A.

Evaluation Criterion: The study will be considered successful if the study demonstrates a 50% reduction or more for all four primary BoExp in the THS 2.2 arm compared to the CC arm (as measured on Day 5).

Secondary Endpoints:

- To determine the reduction of secondary BoExp on Day 5 in smokers switching from CC to THS 2.2 as compared to smokers continuing to smoke CC.
 - BoExp listed as secondary (Table S1) for the comparison of levels between smokers switching from CC to THS 2.2 and smokers continuing to smoke CC as measured on Day 5 as follows:
 - CO (expressed as ppm) in exhaled breath.
 - Urinary BoExp (expressed as quantity excreted and concentration adjusted to creatinine) in 24-hour urine
- To describe the levels of primary and secondary BoExp over the exposure period in smokers switching from CC to THS 2.2 as compared to smokers continuing to smoke CC.
 - BoExp listed as primary and secondary (Table S1) for the comparison of levels between smokers switching from CC to THS 2.2 and smokers continuing to smoke CC as measured from Day 1 to Day 5.
 - CO (expressed as ppm) in exhaled breath.
 - COHb in blood (expressed as % saturation of hemoglobin).
 - Urinary BoExp (expressed as quantity excreted and concentration adjusted to creatinine) in 24 hour urine.
- To determine the levels of nicotine on Day 5 in smokers switching from CC to THS 2.2 as compared to smokers continuing to smoke CC and to describe their levels over the exposure period from Day 1 to Day 5.

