Confidentiality statement: Data and information contained in this document are considered to constitute trade secrets and confidential commercial information, and the legal protections provided to such trade secrets and confidential information are hereby claimed under the provisions of applicable law. No part of this document may be publicly disclosed without the written consent of Philip Morris Products S.A.

- Subject is aged from 23 to 65 years (inclusive).
- Smoking, healthy subject as judged by the investigator is Japanese.
- Subject smokes at least 10 commercially available non-menthol CCs per day (no brand restrictions) for the last 4 weeks, based on self-reporting.
- Subject has smoked for at least the last 3 consecutive years.
- Subject does not plan to quit smoking in the next 3 months.
- The subject is ready to accept interruptions to smoking for up to 5 days.
- The subject is ready to accept using the THS 2.2.

Subjects who do not complete the study after randomization will not be replaced.

Investigational Product; Dose; and Mode of Use:

Test Product: Tobacco Heating System 2.2 (THS 2.2)

Reference Product: The reference product to the THS 2.2 during the randomized exposure period is the subject's own preferred commercially available single brand of CC

Reference Point: Smoking abstinence

Duration of Study:

The entire study duration per subject will be 17 to 44 days, including a Screening period of up to 28 days prior to baseline (Day -30 to Day -3), an 9-day confinement period (from Day -2 to time of Discharge on Day 6), followed by a 7-day safety follow-up period (until Day 13).

Expected Duration of the Entire Study:

1st of July 2013 until 31st January 2014

Statistical Methods:Statistical Analysis:

Analysis of BoExp will be conducted on the natural log scale. The transformed data will be analyzed by means of a generalized linear model using randomized arm as covariate adjusting for the following baseline information: sex, average cigarette consumption over the previous 4 weeks, and baseline value of endpoint. Estimates of differences between groups will be back-transformed to provide relative effects. Assumptions of the ANOVA model will be tested. Markedly non-lognormally distributed BoExp data will be transformed or analyzed by appropriate non-parametric methods.

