7.5.1.2 Plasma Nicotine and Cotinine

Nicotine and cotinine concentrations will be measured in plasma to evaluate the exposure to nicotine. For subjects in the SA arm, blood samples will be collected on Days 0 to 4, at comparable time points. No nicotine PK profile will be done for subjects in the SA arm on Day 5 and Day 6.

- On Day 0 to Day 4 (all study arms):

One blood sample for nicotine and cotinine will be drawn each day between 08:00 PM-09:30 PM.

- Nicotine/cotinine PK Profile on Day 5 and Day 6 (THS 2.2 and CC arms only):

In total, 9 blood samples will be drawn on Day 5. The first blood sample on Day 5 will be drawn within 15 minutes prior to the first product use (=T0). On Day 5, T0 will serve as a

Confidentiality statement: Data and information contained in this document are considered to constitute trade secrets and confidential commercial information, and the legal protections provided to such trade secrets and confidential information are hereby claimed under the provisions of applicable law. No part of this document may be publicly disclosed without the written consent of Philip Morris Products S.A.

reference for the time to peak concentration. An additional 8 blood samples will be drawn in 2-hour intervals after T₀. The last blood sample should be drawn no later than 11:00 PM, corresponding to the end of the product use period. At all time-points, if the subject wants to smoke around the time of the blood draw, he/she should smoke first and the blood will be drawn after the product has been used. Depending on the time of the first product use, it may be that fewer than 8 blood samples will be collected from a subject after T₀.

On Day 6, two blood samples will be drawn. The first one will be 20 hours after T₀ and the second blood sample will be 24 hours after T₀ (with T₀ being the time of the first product use on Day 5).

- On Day 5 and Day 6 (SA arm only):

On Day 5, one blood sample will be drawn between 08:00 PM-09:30 PM.

On Day 6, one blood sample will be drawn between 08:00 AM-09:30 AM.

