Appendix 1 Schedule of Events

Table A1. Study Assessments (separate table [Table A2] shown for 24-hour urine collections)

Study Day	Screening	Confinement Period									Safety Follow-Up ^P	
	-30 to -3	-2	-1	0	1	2	3	4	5	6	7-14	
Informed consent for study participation and two informed consents for bio-banking	•											
Admission/Discharge		•								•		
Advice on the risk of smoking and debriefing	•	•								•		
Support for SA arm					•	•	•	•	•			
Inclusion/exclusion criteria	•	•										
Enrolment		•										
Randomization				•								
Demographics, medical history, concomitant diseases	•											
Vital signs ^a	•	•	•	•	•	•	•	•	•	•		
Physical examination ^b	•	•								•		
Spirometry ^c	•			•						•		
Prior/concomitant medication	•	•	•	•	•	•	•	•	•	•	•	
B/U: Hematology, clinical chemistry, urine analysis	•			•						•		
Electrocardiogram	•									•		

Confidentiality statement: Data and information contained in this document are considered to constitute trade secrets and confidential commercial information, and the legal protections provided to such trade secrets and confidential information are hereby claimed under the provisions of applicable law. No part of this document may be publicly disclosed without the written consent of Philip Morris Products S.A.

Study Day	Screening	Confinement Period									Safety Follow-Up ^p
	-30 to -3	-2	-1	0	1	2	3	4	5	6	7-14
Chest X-ray ^d	•										
B: HIV, hepatitis B and C	•										
U: Urine drug screen, urine cotinine screening test	•	•									
U: Pregnancy test	•	•								•	
Alcohol breath test	•	•									
FTND	•										
Smoking history	•	•									
Willingness to quit smoking ^e	•	•									
Identification of cigarette brand	•	•									
THS 2.2 demonstration	•										
THS 2.2 product test ^f		•									
CO breath test ^g		•	•	•	•	•	•	•	•	•	
B: BoExp in blood: COHb ^h			•	•	•	•	•	•	• (x4)		
B: Biomarker of exposure in plasma: nicotine, cotinine ⁱ				•	•	•	•	•	•	•	
B: CYP1A2 activity				•					•		
B: CYP2A6 activity				•						•	
QSU-brief questionnaire ^j			•	•	•	•	•	•	•		
MNWS (revised version) ^k				•	•	•	•	•	•	•	
MCEQ (modified version; THS 2.2 and CC arms) ^l			•	•	•	•	•	•	•		
HST (THS 2.2 and				•	•			•			

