12.6 Planned Statistical Analyses

Markedly non-lognormally distributed BoExp data will be transformed or analyzed by appropriate non-parametric methods with bootstrapping using the SAS procedure PROC SURVEYSELECT. The seed to be used in any analysis will be contained in the SAS output and will be different for each analysis.

For all statistical analysis data from all arms, THS 2.2, CC and SA will be included in all models.

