12.6.2.2 Nicotine and Cotinine Concentrations

The change from the Day 0 sample will be calculated for the Day 5 sample closest to 08:00 PM only. The concentrations of nicotine and cotinine will be listed and summarized along with this change. Line graphs of the nicotine and cotinine concentration profiles across all study days showing mean and 95% CI will also be produced.

For nicotine and cotinine plasma concentrations the change from baseline (Day 0 sample at 08:00 PM - 09:30 PM) on the Day 5 sample closest to 08:00 PM will be analyzed using an ANCOVA model with terms for baseline (Day 0) concentration, sex, average daily CC consumption over the last 4 weeks as reported during screening and product. No adjustment will be made for multiple comparisons.

The SAS code to be used is shown below:

```
Proc mixed data=_data_ ;  
Class product sex cigarette_cons time_point ;  
Model change from baseline = baseline sex cigarette_cons product ;  
Lsmean product / diff alpha=0.05 cl ;  
Run ;
```

LS means for each product along with the difference (THS 2.2 - CC) and 95% CI will be presented in the tables.

All figures, summaries and analyses will be performed on the FAS only.

The data will be presented in the below outputs, the TFL number refers to the TFL number in the accompanying TFL shell document:

TFL number	Title
FIGURES	
15.1.2.31	Plasma Nicotine Concentrations (ng/mL) Mean and 95% CI on Day 5 – FAS
15.1.2.32	Plasma Cotinine Concentrations (ng/mL) Mean and 95% CI on Day 5 – FAS
TABLES	
15.2.4.40	Descriptive Statistics of Plasma Nicotine Concentrations (ng/mL) – FAS
15.2.4.41	Descriptive Statistics of Plasma Cotinine Concentrations (ng/mL) – FAS
15.2.4.46	Analysis of Change from Day 0 Plasma Nicotine and Cotinine Concentrations at 08:00 PM on Day 5 – FAS
LISTINGS	
15.3.3.4	Listing of Plasma Nicotine Concentrations and Sampling Times
15.3.3.5	Listing of Plasma Cotinine Concentrations and Sampling Times

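### Plasma nicotine and cotinine are analysed as untransformed change with the abstinence arm in the model; this departs from the protocol's log scale, is not declared, and can misstate the nicotine interval in either direction

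*Protocol*

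**What the plan says.** Table S1 (Protocol synopsis and 3.4) places plasma nicotine and plasma cotinine in the group "BoExp to nicotine". The schedule in Appendix 1 has the row "B: Biomarker of exposure in plasma: nicotine, cotinine", and Protocol 7.5.1.2 sits under the biomarker-of-exposure heading 7.5.1.

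For biomarkers of exposure, the synopsis and Protocol 12.4.4 say "Analysis of BoExp will be conducted on the natural log scale", with adjustment for sex, cigarette consumption and the baseline value. They add: "Estimates of differences between groups will be back-transformed to provide relative effects". The protocol gives no separate model for plasma nicotine or cotinine.

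SAP 12.6.2.2 uses "Model change from baseline = baseline sex cigarette_cons product" and states "LS means for each product along with the difference (THS 2.2 - CC) and 95% CI will be presented in the tables". The code has no option for arm-specific variance or slope. SAP 12.6 adds "For all statistical analysis data from all arms, THS 2.2, CC and SA will be included in all models". The SA arm does have a matching sample: "On Day 5, one blood sample will be drawn between 08:00 PM-09:30 PM" (Protocol 7.5.1.2). SAP Section 9, which lists changes from the protocol, does not mention the change of scale.

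**The concern.** There are two separate matters.

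- **Scale and effect measure.** The protocol leads the reader to expect a ratio from a log-scale model. The SAP delivers a difference in ng/mL without saying that this is a departure. NEQ, listed under the same secondary objective, is log-transformed in SAP 12.6.2.1, so one objective is analysed on two scales.
- **The SA arm.** Smoking stops at 11:00 PM on Day 0 and the Day 5 sample is due from 08:00 PM, so SA has been without tobacco for 5 × 24 − 3 = 117 hours. If its nicotine is then near zero, 40 subjects with almost no Day 5 variation feed the single residual variance and the single slope behind the THS 2.2 versus CC interval.

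Whether THS 2.2 delivers less nicotine than CC is a named secondary objective and bears on how the exposure reductions are read.

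**Working it through.** **1. The plan's own figures.** The documents give no SD, CV, correlation, power or precision for plasma nicotine or cotinine. The nearest stated figure is Protocol Table 18, YVD-CS01-EU row, for the four primary biomarkers. I used log SD = √ln(1+CV²), distance ln((1−reduction)/MR), 80 versus 40 subjects and one-sided 2.5%, and multiplied the four powers. This gives 95.8, 91.8, 85.4, 75.9, 63.5 and 49.2%, against 96, 91, 85, 75, 63 and 48% stated. The row is reproduced to within 1.2 points. It shows that the plan's own planning treats biomarkers of exposure as log-normal and compares them by ratios.

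**2. Effect of pooling SA, equal SDs in the two product arms.** Allocation is 80/40/40. Within-arm degrees of freedom, ignoring covariates, are 118 for two arms and 157 for three, so w = 118/157 = 0.7516 and w(1−w) = 0.1867. Let ρ be the Day 0 to Day 5 correlation in the product arms, and take SA as constant on Day 5. The pooled slope is then w times the product-arm slope. In units of the Day 5 variance:

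- two-arm residual variance: 1−ρ²
- three-arm residual variance: w(1−ρ²) + w(1−w)ρ²
- width ratio, three-arm to two-arm: √[w + w(1−w)ρ²/(1−ρ²)]

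At ρ = 0: √0.7516 = 0.867. At 0.5: √(0.7516 + 0.1867×0.3333) = 0.902. At 0.7: 0.965. At 0.9: √(0.7516 + 0.1867×4.263) = 1.244. The widths are equal when ρ²/(1−ρ²) = 1/w, that is at ρ = 0.756.

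Equal width is not quite correct width, because the pooled slope is wrong for the product arms. Their true residual variance is (1−ρ²) + (1−w)²ρ². Reported and true variance agree when ρ² = 1/(2w) = 157/236 = 0.665, so ρ = 0.816. Below that the interval is too narrow; above it, too wide.

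**3. Effect of the raw scale.** If both arms have the same CV, a true ratio of 0.6 makes the THS 2.2 SD 0.6 times the CC SD, and the smaller arm has the larger variance. Ignoring baseline, with the CC SD set to 1:

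- true variance of the difference: 0.36/80 + 1/40 = 0.0295
- raw, two arms: (79×0.36 + 39)/118 × (1/80 + 1/40) = 0.0214, so the SE ratio is √(0.0214/0.0295) = 0.852
- raw, three arms: the same with divisor 157 gives 0.0161, SE ratio 0.739 (= 0.852 × 0.867)

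Both the scale and the pooling contribute. Other SD patterns go the other way: the three-arm SE ratio is 0.987 at a THS/CC SD ratio of 1.5 and 1.063 at 2.

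**4. Simulated coverage of the nominal 95% interval.** Assumed: log-normal nicotine, CV 40-80%, ρ 0.4-0.9, SA near zero on Day 5.

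| True THS:CC ratio | As written (raw, three arms) |
|---|---|
| 0.6 | 84-91% |
| 0.8 | 89-94% |
| 1.0 | 91-97% |
| 1.2 | 94-99% |

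Repeating the simulation moves the ends by one to two points. For comparison:

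- The raw two-arm model covers 88-92% at ratio 0.6.
- The log model with SA held at a constant covers 91-97%.
- The log model with THS 2.2 and CC only covers 94-97% in every setting.
- If SA values are quantifiable and vary on the log scale, the three-arm log interval is 1.05 to 1.98 times the two-arm width.

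Logging alone is therefore not a cure.

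**The case against.** The best defence is that the protocol rule may not bind here. Table S1 keeps the nicotine markers apart from the primary and secondary biomarkers, and the hypothesis in Protocol 12.4.4 names only those two groups. Protocol 7.5.1.3 and SAP 12.6.2.1 count NEQ as secondary but do not name the plasma analytes, which may explain the two scales. Protocol 12.5 sets no inferential model for secondary endpoints, and 12.1 leaves detail to the SAP. This softens the charge of contradiction. It does not remove it, because the synopsis sentence is unqualified and nothing in the SAP explains the different treatment. Modelling change rather than the Day 5 value is also harmless: with baseline as a covariate, the arm difference is the same.

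A reader might infer more than the documents support:

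- **That the interval is simply too narrow and the test anti-conservative.** The direction depends on the correlation and the arm SDs, which are not given. With no true difference, coverage of 91-97% means a rejection rate of 3-9%.
- **That the low coverage at ratio 0.6 is all due to pooling SA.** The raw scale alone already brings it to 88-92%.
- **That cotinine is affected in the same way.** The documents give no cotinine half-life, and near-zero SA values are argued for nicotine only.
- **That the result cannot be set beside a planned NEQ ratio.** SAP 12.6.2.1 itself describes a THS 2.2 minus CC difference for the secondary biomarkers including NEQ, and geometric means are planned for log-normal data, so an unadjusted ratio could be derived.

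**Conclusion.** The point stands in this form. There is an undeclared change of scale and effect measure for both analytes. For nicotine, a common-variance, common-slope model that includes SA can misstate the THS 2.2 versus CC interval in either direction. The conflict between the documents needs no assumption. The coverage figures rest on log-normal data, equal CVs across the product arms, the stated ranges of CV and correlation, and SA near zero on Day 5, none of which the documents supply. Within those ranges, undercoverage is clearest if THS 2.2 delivers less nicotine than CC. If delivery is equal or higher and the correlation is high, the interval can be about right or too wide. As a secondary endpoint with no success criterion, this should be fixed but does not touch the primary conclusion.

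**What to change.** In SAP 12.6.2.2, model log(Day 5) with log(Day 0), sex, cigarette consumption and product, using the THS 2.2 and CC arms only, and state this as an exception to the all-arms sentence in SAP 12.6. Back-transform and report the THS 2.2 : CC ratio with its 95% CI. Summarise SA descriptively, and retitle Table 15.2.4.46, which now refers to change from Day 0. The LLOQ/2 rule in SAP 7.1 already deals with values that could not otherwise be logged.

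If the sponsor prefers the arithmetic difference, the minimum is to declare and justify it in Section 9, and either to leave SA out of the comparison or to allow arm-specific variances and slopes.

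The cost is one code block, one sentence and a table title. The small loss is a model-based SA estimate for these two analytes, which the THS 2.2 versus CC objective does not need.
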